Results from Part 2 data snapshot as of 01 May 2023, show robust nAb responses 28 days after 1 dose of 50 µg mRNA-1273 in baseline SARS-CoV-2 positive participants. After 28 days post dose 1 of 50 µg mRNA-1273, the GMC levels in the adolescent baseline-positive participants increased to 18-fold higher than the baseline GMC levels (GMC=6053.2 [95%CI: 4495.8, 8150.1]). Despite the higher baseline nAb responses observed in adolescent baseline-positive participants, the GMC post dose 1 of 50-µg mRNA-1273 was observed to be higher than those observed post primary series in baseline SARS-CoV-2 negative young adults in Study P301 (GMC=1400.4 [95% CI: 1272.7, 1541.0] with a GMR of 4.322 (95% CI: 3.274, 5.707). The seroresponse rates were comparable between the Study P203 adolescents (97.5%, n=39/40) and Study P301 young adults (99.3%, n=292/294), with SRR difference of -1.8% (95% CI: -12.2%, 0.8%). Administration of the second dose did not increase the neutralizing antibody response to the degree which was observed in baseline SARS-CoV2 negative participants (mRNA-1273 Part 2 Data Memo).

Results from Part 3 IA (data cutoff of 05 Jun 2023) demonstrate that after 28 days post Dose 1 of 50 µg mRNA-1273.222, the GMC levels against the Omicron BA.4/BA.5 in the adolescent baseline-positive participants increased to 18-fold higher than the baseline GMC levels (GMC=2771.0 [95% CI: 2500.8, 3070.3]). The GMC post Dose 1 of 50 µg mRNA-1273.222 was observed to be higher than those observed post-primary series in baseline SARS-CoV-2 negative young adults in Study P301 (GMC=56.6 [95% CI: 54.5, 58.8]). The rate of seroresponse against the Omicron BA.4/BA.5 was high (94.7%) in study P203 Part 3 adolescents whereas none of the P301 young adults seroconverted against the Omicron BA.4/BA.5, 28 days after Dose 2 of the 100 µg mRNA-1273 primary series; the difference in SRR was 94.7% (95% CI: 91.1%, 96.9%). In addition, the GMC levels against the ancestral strain in the adolescent baseline-positive participants increased to 13.6-fold 28 days post Dose 1 compared to baseline GMC levels (Day 29 GMC=7187.1 [95% CI: 6495.3, 7952.7]). The GMC post Dose 1 of 50 µg mRNA-1273.222 in adolescent baseline-positive participants was observed to be higher than those observed post-primary series in baseline SARS-CoV-2 negative young adults in

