Study P301 (GMC=1692.3 [95% CI: 1537.4, 1862.7]). The rates of seroresponse against the ancestral strain were comparable between the study P203 Part 3 adolescents (94.6%) and study P301 young adults (99.3%); the difference in SRR was -4.7% (95% CI: -8.4%, -2.1%). The GMR of Study P203 Part 3 Day 29 GMC against Omicron BA.4/BA.5 compared with young adults in Study P301, Day 57 GMC was 48.953 (95% CI: 44.209, 54.206), meeting the superiority criterion (ie, lower bound of the 95% CI >1.0). The GMR of Study P203 Part 3 Day 29 GMC against ancestral strain compared with young adults in Study P301, Day 57 GMC was 4.247 (95% CI: 3.693, 4.884), meeting the noninferiority criterion (ie, lower bound of the 95% CI >0.667). The prespecified success criteria for the primary immunogenicity objective were met, thus enabling the inference of vaccine effectiveness of the single 50 µg mRNA-1273.222 in Study 203 Part 3 from that observed in Study P301.

Based on Part 3 IA results and the approval of the updated monovalent COVID-19 vaccine containing the spike proteins for the XBB.1.5 sublineage of SARS-CoV-2, the second dose in Part 3 was removed.

In the post-EUA period, anaphylaxis has been reported following mRNA-1273 administration. There have been very rare reports of myocarditis and pericarditis occurring after vaccination with COVID-19 mRNA vaccines. A detailed review of the clinical experience with LNPs containing SM-102 (mRNA vaccines and placebo) is provided in the IB.

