8.3.1.2.2. Part 1C-2 – Heterologous Booster Phase

Approximately 362 participants who received non-Moderna COVID-19 vaccine as primary series vaccination at least 3 months prior were planned to be enrolled to receive mRNA-1273 50 μ g as heterologous booster in Part 1C-2. However, the study population in Part 1C-2 will have less than the planned number of participants enrolled, as a result of slow enrollment and discontinuation of recruitment in Part 1C-2 ([Section 3.1.1.4](#)).

8.3.2. Part 2

Approximately 362 participants were planned to be enrolled to receive mRNA-1273 50 µg in the open-label Part 2. However, the study population in Part 2 will have less than the planned number of participants receiving at least one dose of 50 µg mRNA-1273, with a small sample size as a result of slow enrollment and discontinuation of recruitment in Part 2 ([Section 3.1.2](#)).

8.3.3. Part 3

With at least 300 adolescents enrolled in Part 3 to receive 50 µg mRNA-1273.222, the study will have at least a 95% probability to observe at least 1 participant with an AE at a true AE rate of 1%.

Assuming a true serum Ab GMR of 1.6 for GM value against Omicron BA.4/BA.5 at Day 29 after Dose 1 of mRNA-1273.222 in baseline SARS-CoV-2 positive adolescents compared with GM value against Omicron BA.4/BA.5 at Day 57 after Dose 2 of mRNA-1273 primary series in young adults who are baseline SARS-CoV-2 negative in P301, with approximately 168 participants in the PP Immunogenicity Subset who are baseline SARS-CoV-2 positive in P203 Part 3 and 300 young adults in P301 who are baseline SARS-CoV-2 negative, there will be at least >90% power to demonstrate superiority of the serum Ab GM value against Omicron BA.4/BA.5 after Dose 1 of mRNA-1273.222 in adolescents in P203 to that after Dose 2 of mRNA-1273 in young adults in Study P301 at two-sided α of 0.05 using a superiority margin of 1.0. The standard deviation of the natural log transformed levels of Ab is assumed to be 1.5.

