8.5.8. Part 3 Analysis

In the safety analysis, the number and percentage of participants with unsolicited AEs, severe AEs, treatment-related AEs, SAEs, MAAEs, AESIs, and AEs leading to discontinuation from the study participation in Part 3 will be summarized.

The number and percentage of participants with any solicited local AR, with any solicited systemic AR, and with any solicited AR during the 7-day follow-up period after each injection will be provided.

In the Part 3 immunogenicity analysis, for the coprimary endpoints (Ab GM value against Omicron BA.4/BA.5 and the ancestral strain at Day 29 after Dose 1 of 50 µg mRNA-1273.222 in baseline SARS-CoV-2 positive adolescents in Study P203 compared with those at Day 57 after Dose 2 of 100 µg mRNA-1273 in baseline SARS-CoV-2 negative adults 18 to 25 years of age in Study P301), the following analyses will be performed for the respective hypothesis testing:

An ANCOVA model will be carried out with Ab value at Day 29 in P203 and Ab value at Day 57 in P301 as a dependent variable and a group variable (baseline SARS-CoV-2 positive adolescents in Study P203 and baseline negative SARS-CoV-2 young adults in Study P301) as the fixed variable, where a covariate may be included in the model (to be specified in the SAP). The GM value at Day 29 in P203 and the GM value at Day 57 in P301, and respective GMR for P203 compared to P301 will be estimated from the model. A corresponding 2-sided 95% CI of GMR estimated from the ANCOVA model will be provided to assess the difference in immune response after Dose 1 (Day 29) for the adolescents in Study P203 compared to that after Dose 2 (Day 57) in the young adults (18 to 25 years of age) in Study P301.

The first coprimary endpoint, superiority of immune response to mRNA-1273.222 against Omicron BA.4/BA.5 after Dose 1 compared to mRNA-1273 against Omicron BA.4/BA.5 after Dose 2 as measured by GM value will be considered demonstrated if the respective GMR 95% CI lower bound is >1 based on a superiority margin of 1.

The second coprimary endpoint, noninferiority of immune response to mRNA-1273.222 against ancestral strain after Dose 1 compared to mRNA-1273 against the ancestral strain after Dose 2 as

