8.6. Multiplicity Adjustment

A hierarchical sequential hypothesis testing (fixed-sequence) method will be used to adjust multiplicity to preserve the family-wise type I error rate ($\alpha = 0.05$). The hypothesis testing for the 2 coprimary endpoints (GMT and SRR) for the primary series of mRNA-1273 in Part 1A was completed and statistically significant based on data snapshot dated 08 May 2021, and thus the α level of 0.05 can be passed to Part 1C-1 hypothesis testing. In Part 1C-1 Homologous Booster Phase, the hypothesis testing for the 2 coprimary endpoints (GMT and SRR against the ancestral strain) after BD of mRNA-1273 will be tested at α level of 0.05. The testing in Part 1A and 1C-1 will continue through the sequence only until an endpoint is not statistically significant (did not meet specified noninferiority success criteria), in which case the testing will stop. If the hypothesis testing for the 2 coprimary endpoints in Part 1C-1-Homologous Booster Phase is statistically significant (meeting the noninferiority success criteria of the coprimary endpoints), the α level of 0.05 will be passed to the hypothesis testing in Part 3.

For the key secondary objective in Part 1C-1 Homologous Booster Phase to evaluate immune response elicited by the 50 μ g prototype booster of mRNA-1273 against variant(s) of interest, the key secondary endpoints will be analyzed independently, given that prototype vaccine mRNA-1273 does not contain variant specific sequences.

Part 3

Since the hypothesis testing for the coprimary endpoints in Part 1C-1 was statistically significant based on an IA with a data cutoff dated 16 May 2022, the α level of 0.05 (two-sided) was passed to Part 3 hypothesis testing.

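### The co-primary 1 GMR interval is estimated with no allowance for unequal variances, and the printed BA.4/BA.5 interval is about 7% too narrow as a result; no conclusion changes

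*Protocol*

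**What the plan says.** Section 8.5.8, repeated in the synopsis under Part 3 Analyses, models the antibody values of both studies in one ANCOVA with study group as the fixed effect. The decision interval comes from that model: "A corresponding 2-sided 95% CI of GMR estimated from the ANCOVA model will be provided". For co-primary 1 the margin is a ratio of unity, and superiority "as measured by GM value will be considered demonstrated if the respective GMR 95% CI lower bound is >1 based on a superiority margin of" that value. Section 8.6 sets the level: "the α level of 0.05 (two-sided) was passed to Part 3 hypothesis testing".

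The one model element deferred is the covariate: "where a covariate may be included in the model (to be specified in the SAP". Variance structure is not mentioned. Section 8.5.8 also plans a t-distribution summary of the GMR, but does not say whether it pools variances, and that summary does not decide the endpoint.

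Section 8.3.3 plans with one spread for both groups, "The standard deviation of the natural log transformed levels of Ab is assumed to be 1.5", and with "168 participants in the PP Immunogenicity Subset who are baseline SARS-CoV-2 positive in P203 Part 3 and 300 young adults in P301".

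Section 1.2.2.5 reports the Part 3 interim result. The adolescent BA.4/BA.5 geometric mean is 2771.0 (95% CI 2500.8 to 3070.3). The adult comparator is given as "Study P301 (GMC=56.6 [95% CI: 54.5, 58.8". The GMR "was 48.953 (95% CI: 44.209, 54.206), meeting the superiority criterion".

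**The concern.** An ANCOVA in its usual form estimates one residual variance and applies it to both groups. That is harmless when the spreads are alike or the groups are of equal size. When the smaller group is also the more variable one, pooling understates the standard error of the difference and the interval is too short.

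The BA.4/BA.5 comparison looks like that case. The adult interval is very tight around a low value, and Section 1.2.2.5 says that no P301 adult seroconverted against this strain, whereas the adolescents vary widely. At stake is the stated precision of a co-primary estimate that the protocol uses to infer effectiveness and to justify removing Dose 2. The same model text governs the final analysis.

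**Working it through.** **Inputs.** All intervals are from Section 1.2.2.5. The log half-width of an interval (L, U) is h = ln(U/L)/2.

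| Quantity | Estimate (95% CI) | h |
|---|---|---|
| BA.4/BA.5, adolescents | 2771.0 (2500.8, 3070.3) | 0.1026 |
| BA.4/BA.5, P301 | 56.6 (54.5, 58.8) | 0.0380 |
| BA.4/BA.5, GMR | 48.953 (44.209, 54.206) | 0.1019 |
| Ancestral, adolescents | 7187.1 (6495.3, 7952.7) | 0.1012 |
| Ancestral, P301 | 1692.3 (1537.4, 1862.7) | 0.0960 |
| Ancestral, GMR | 4.247 (3.693, 4.884) | 0.1398 |

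**Check that needs no sample size.** For two independent groups the log variances add, so the half-width of the ratio should be close to √(h₁² + h₂²).

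- BA.4/BA.5: √(0.1026² + 0.0380²) = 0.1094 (0.1091 to 0.1097 over rounding of the printed bounds). Reported: 0.1019, below even the adolescent 0.1026.
- Implied interval: 48.953 × exp(±0.1094) = 43.9 to 54.6.
- Ancestral control: √(0.1012² + 0.0960²) = 0.1395, against 0.1398 reported.

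The discrepancy appears only for the strain where the spreads differ.

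**Is it a covariate effect?** The raw ratios are 2771.0/56.6 = 48.96 and 7187.1/1692.3 = 4.247. Both match the reported GMRs, so no adjustment is visible.

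**Do the two group intervals themselves come from the pooled model?** If they shared one variance, their squared half-widths would be nearly in inverse ratio to the group sizes. Here (0.1026/0.0380)² = 7.3, far from any plausible size ratio. They carry each group's own variance.

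**Reproducing the reported interval.** Group sizes at the Part 3 interim are not stated. The P301 size is taken as 294, the denominator given for the Part 2 comparison. The adolescent size is inferred: a Miettinen-Nurminen interval against 0/294 reproduces the reported BA.4/BA.5 seroresponse difference of 94.7% (91.1% to 96.9%) at 231/244 or 232/245. The reported GMR interval itself is matched best at 243.

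With SE = h/t and SD = SE × √n, for 243 and 294:

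- Adolescents: SE = 0.1026/1.970 = 0.0521; SD = 0.81.
- P301: SE = 0.0380/1.968 = 0.0193; SD = 0.33.
- Pooled SD = √[(242 × 0.812² + 293 × 0.331²)/535] = 0.598.
- Pooled SE = 0.598 × √(1/243 + 1/294) = 0.0519; times t = 1.964 gives h = 0.1019, interval **44.21 to 54.20**. With 245 adolescents it is 44.20 to 54.22. Reported: 44.209 to 54.206.
- Unequal-variance SE = √(0.0521² + 0.0193²) = 0.0555; Welch h = 0.1093, interval **43.89 to 54.61**.

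The reported interval is the pooled one.

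**Coverage.** The reported half-width is 0.1019/0.0555 = 1.84 correct standard errors, so coverage is 2Φ(1.84) − 1, about 93.4%. Relative width: 0.1019/0.1093 = 0.933, about 7% too narrow.

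**Direction.** Holding the SDs at about 0.815 and 0.33 against 294 adults, pooled-interval coverage is 93.4% with 245 adolescents, 94.3% with 270, 95.0% with 294 and 95.7% with 320. Pooling errs on the short side only while the adolescent group is the smaller.

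**The case against.** The best counter-argument is that the protocol never says equal variance. Section 8 sends analysis detail to the SAP, and residual-variance structure is the kind of detail that belongs there. The evidence is an interim result in a background section. Part of this stands: the pooled reading is an inference. But Section 8.5.8 fixes both the model and the interval that decides the endpoint, and defers only the covariate. The printed result shows what that text produced in practice.

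The second argument is that nothing turns on it. This stands in full. The lower bound moves from 44.2 to 43.9 against a threshold of 1. On the log scale the estimate is ln(48.953)/0.0555, about 70 standard errors, from that threshold.

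Three stronger readings are tempting, and the documents support none of them.

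- A reader might put the observed SDs into the planned 168 versus 300, obtain a pooled SE of 0.0535 against a correct 0.0656, and conclude that coverage is about 89% and the one-sided error more than doubled. The inferred interim size is well above 168. A type I error claim would also need the same SD imbalance at a true GMR of 1. Section 1.2.2.5 shows that imbalance only alongside a 49-fold difference, with the adults' response to this strain minimal; nothing shows it would persist at the null.
- A reader might infer that the final interval must also under-cover. Part 3 enrols at least 300, Section 8.7.1 lets an interim cover all or a subset of participants, and the final per-protocol baseline-positive number is not given. At about 294 or more the shortfall disappears.
- A reader might extend the point to other variants of interest. The protocol gives no P301 titres for them in Part 3 and prescribes the ANCOVA only for the two co-primary endpoints.

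**Conclusion.** The point holds as a defect of reported precision and of the specified method. The BA.4/BA.5 GMR interval is about 7% too narrow on the log scale: 44.2 to 54.2 printed, against about 43.9 to 54.6 implied by the protocol's own group intervals. That finding needs no sample size and is firm. The coverage figure of about 93.4% is less firm, because it rests on an adolescent size inferred from another interval and on 294 adults carried over from Part 2. That carry-over is an assumption: the adult ancestral geometric mean printed for Part 2 (1400.4) differs from the one printed for Part 3 (1692.3).

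Superiority against BA.4/BA.5 is not in doubt. The ancestral noninferiority result is unaffected, with SDs of about 0.80 and 0.84. No inflation of the trial's error rate is shown. The reason to act is that a co-primary interval visibly shorter than one of its own components should not be carried into the final report.

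**What to change.** In Section 8.5.8 and the matching synopsis text, state that the GMR and its 95% CI are estimated with group-specific residual variances and Satterthwaite degrees of freedom, which is the Welch interval when no covariate is used. Carry the same sentence into the SAP, and report the BA.4/BA.5 interval on this basis in the final analysis.

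The cost is one model option and one sentence. At the interim sizes the BA.4/BA.5 interval becomes slightly wider, so the change cannot be read as favouring the sponsor. The ancestral half-width barely moves (0.1392 by Welch against 0.1398 reported). No new data are needed, and both co-primary conclusions stay as they are.

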8.5.9. Exploratory Analyses

Exploratory analyses will be described in the SAP before database lock.

8.5.10. Subgroup Analyses

Subgroup analyses will be performed as described in the SAP.

8.6. Multiplicity Adjustment

A hierarchical sequential hypothesis testing (fixed-sequence) method will be used to adjust multiplicity to preserve the family-wise type I error rate ($\alpha = 0.05$). The hypothesis testing for the 2 coprimary endpoints (GMT and SRR) for the primary series of mRNA-1273 in Part 1A was completed and statistically significant based on data snapshot dated 08 May 2021, and thus the α level of 0.05 can be passed to Part 1C-1 hypothesis testing. In Part 1C-1 Homologous Booster Phase, the hypothesis testing for the 2 coprimary endpoints (GMT and SRR against the ancestral strain) after BD of mRNA-1273 will be tested at α level of 0.05. The testing in Part 1A and 1C-1 will continue through the sequence only until an endpoint is not statistically significant (did not meet specified noninferiority success criteria), in which case the testing will stop. If the hypothesis testing for the 2 coprimary endpoints in Part 1C-1-Homologous Booster Phase is statistically significant (meeting the noninferiority success criteria of the coprimary endpoints), the α level of 0.05 will be passed to the hypothesis testing in Part 3.

For the key secondary objective in Part 1C-1 Homologous Booster Phase to evaluate immune response elicited by the 50 μ g prototype booster of mRNA-1273 against variant(s) of interest, the key secondary endpoints will be analyzed independently, given that prototype vaccine mRNA-1273 does not contain variant specific sequences.

Part 3

Since the hypothesis testing for the coprimary endpoints in Part 1C-1 was statistically significant based on an IA with a data cutoff dated 16 May 2022, the α level of 0.05 (two-sided) was passed to Part 3 hypothesis testing.

8.7. Study Analyses

8.7.1. Interim Analyses

More than one IA may be performed.

- The IA of immunogenicity, safety, and efficacy will be performed after Day 57 immunogenicity data are available for the Immunogenicity Subset and at least 1500 participants (1,000 participants receiving mRNA-1273) have completed Day 57 (1 month after Dose 2, Part 1A). This IA will be considered the primary analysis of immunogenicity for Part 1A.
- An IA of immunogenicity and safety may be performed after all or subset of participants who receive BD have completed BD-Day 29 after the BD in Part 1C-1.
- An IA of immunogenicity and safety may be performed after all or subset of participants who receive heterologous BD have completed BD-Day 29 after the BD in Part 1C-2.
- An IA of immunogenicity and safety may be performed after Day 57 immunogenicity data are available after all or a subset of participants in Part 2 have completed Day 57 (1 month after Dose 2, Part 2).
- An IA of immunogenicity and safety may be performed after all or a subset of participants who receive 50 μ g mRNA-1273.222 dose have completed Day 29 (1 month after Dose 1).
- At the Sponsor's discretion, a CSR may be developed for an IA.

8.7.2. Final Analysis

The final analysis of all applicable endpoints will be performed after all participants have completed all planned study procedures. Results of this analysis will be presented in a final CSR, including individual listings.

Additional information about all study analyses may be provided in the SAP.

10. SUPPORTING DOCUMENTATION AND OPERATIONAL CONSIDERATIONS

10.1. APPENDIX 1: Schedule of Assessments

The schedules of assessments are presented in [Table 10](#) for Part 1A, [Table 12](#) for Part 1B, [Table 13](#) for Part 1C-1, [Table 14](#) for Part 1C-2, [Table 15](#) for Part 2 participants who receive the booster dose, [Table 16](#) for Part 2 participants who do not receive the booster dose, [Table 17](#) for Part 3 participants who receive Dose 2, and [Table 18](#) for Part 3 participants who receive a single dose.

If a participant cannot attend a study site visit (scheduled or unscheduled) with the exception of Screening or Day 1, a home visit is acceptable if performed by appropriately delegated study site staff or a home healthcare service provided by the Sponsor ([Section 7](#)). If neither a participant visit to the study site nor a home visit to the participant is possible (with the aforementioned exceptions), a safety telephone call should be performed that includes the assessments scheduled for the safety telephone calls.

After the Participant Decision Clinic Visit, participants will continue to follow the Part 1A SoA ([Table 10](#)) or Part 1B SoA ([Table 12](#)), as described in [Section 3.1.1.2](#) and as shown in [Figure 10](#). All eligible participants will be offered a BD and those who choose to receive BD will follow Part 1C-1 SoA ([Table 13](#)). Eligible participants that completed their primary COVID-19 vaccination series under EUA and choose to receive a BD will follow Part 1C-2 SoA ([Table 14](#)). Eligible participants enrolled in Part 2 will follow Part 2 SoA ([Table 15](#) and [Table 16](#)). Eligible participants enrolled in Part 3 will follow Part 3 SoA ([Table 17](#) and [Table 18](#)).

Table 10: Schedule of Assessments Part 1A, the Blinded Phase; Part 1B Open-label Observational Phase for Participants who Received mRNA-1273 in Part 1A

Visit Number	0	1	2	3	4	5	-	6	-	7		
Type of Visit	C	C	Virtual Call	C	Virtual Call	C	SFU	C	SFU	C		
Month Timepoint		M0		M1		M2	eDiary	SC	M7	eDiary	SC	M13
Study Visit Day	D0¹ (Screening)	D1 (Baseline)	D8²	D29³	D36^{2,3}	D57^{2,3}	Every 4 weeks D71 – D183^{3,4}	Every 4 weeks D85 – D197^{3,5}	D209/ Participant Decision Visit^{3,6}	Every 4 weeks D223 – D363^{3,4}	Every 4 weeks D237 – D377^{3,5}	D394³
Window Allowance (Days)	- 28		+ 3	+ 7	+ 3	+ 7	±3	± 3	- 56/+ 56	± 3	± 3	± 14
Days Since Most Recent Injection	-	0	7	28/0	7	28	-	-	180	-	-	365
Informed consent/assent form, demographics, concomitant medications, medical history	X											
Revised informed consent/assent form									X			
Review of inclusion and exclusion criteria	X	X										
Physical examination including vital signs, height, weight ⁷	X	X		X		X			X			X
Pregnancy test ⁸	X	X		X								
Randomization		X										
Study injection (including 30-minute post dose observation period)		X		X								

Visit Number	0	1	2	3	4	5	-	6	-	7		
Type of Visit	C	C	Virtual Call	C	Virtual Call	C	SFU	C	SFU	C		
Month Timepoint		M0		M1		M2	eDiary	SC	M7	eDiary	SC	M13
Study Visit Day	D0¹ (Screening)		D1 (Baseline)		D8²	D29³	D36^{2,3}	D57^{2,3}	Every 4 weeks D71 – D183^{3,4}	Every 4 weeks D85– D197^{3,5}	D209/ Participant Decision Visit^{3,6}	Every 4 weeks D223– D363^{3,4}
Window Allowance (Days)	- 28		+ 3	+ 7	+ 3	+ 7	±3	± 3	- 56/+ 56	± 3	± 3	± 14
Days Since Most Recent Injection	-	0	7	28/0	7	28	-	-	180	-	-	365
Blood sample for vaccine immunogenicity ⁹		X				X			X			X
Nasopharyngeal or nasal swab sample for SARS-CoV-2 ¹⁰		X		X		X			X			
Surveillance for COVID-19/ Illness visit ¹¹ / Unscheduled visit		X	X	X	X	X	X	X	X	X	X	X
Convalescent Visit ¹²		X	X	X	X	X	X	X	X	X	X	X
eDiary activation for recording solicited ARs (7 days) ¹³		X		X								
Review of eDiary data			X		X							
Follow-up safety telephone calls ¹⁴								X		X		
Recording of unsolicited AEs		X	X	X	X	X						
Recording of MAAEs and concomitant medications relevant to or for the treatment of the MAAE ¹⁵		X	X	X	X	X	X		X	X		X

Visit Number	0	1	2	3	4	5	-	6	-	7		
Type of Visit	C	C	Virtual Call	C	Virtual Call	C	SFU	C	SFU	C		
Month Timepoint		M0		M1		M2	eDiary	SC	M7	eDiary	SC	M13
Study Visit Day	D0 ¹ (Screening)		D1 (Baseline)		D8 ²	D29 ³	D36 ^{2,3}	D57 ^{2,3}	Every 4 weeks D71 – D183 ^{3,4}	Every 4 weeks D85– D197 ^{3,5}	D209/ Participant Decision Visit ^{3,6}	
Window Allowance (Days)	- 28		+ 3	+ 7	+ 3	+ 7	±3	± 3	- 56/+ 56	± 3	± 3	± 14
Days Since Most Recent Injection	-	0	7	28/0	7	28	-	-	180	-	-	365
Recording of SAEs and concomitant medications relevant to or for the treatment of the SAE ¹⁵		X	X	X	X	X	X	X	X	X		X
Recording of AESI		X	X	X	X	X	X	X	X	X		X
Recording of concomitant medications and nonstudy vaccinations ¹⁵		X	X	X	X	X						
Study completion												X

Abbreviations: AE = adverse event; AESI = adverse event of special interest; AR = adverse reaction; BMI = body mass index; C = clinic visit; COVID-19 = coronavirus disease 2019; D = day; eDiary = electronic diary; FDA = USA Food and Drug Administration; IP = investigational product; IRB = institutional review board; LAR = legally acceptable representative; M = month; MAAE = medically attended AE; NP = nasopharyngeal; SC = safety (telephone) call; SFU = safety follow-up; RT-PCR = reverse transcriptase polymerase chain reaction; SAE = serious adverse event; SARS-CoV-2 = Severe Acute Respiratory Syndrome coronavirus 2.

Note: In accordance with FDA Guidance on Conduct of Clinical Trials of Medical Products during COVID-19 Public Health Emergency ([DHHS 2020](#)), investigators may convert study site visits to home visits or telemedicine visits with the approval of the Sponsor.

Note: If during the Participant Decision Visit ([Table 11](#)) the participant is unblinded and determined to have received 2 doses of mRNA-1273 in Part 1A, due to statistical considerations, they will be considered in the Open-label Observational Phase but will continue to follow the Part 1A SoA.

1. Day 0 and Day 1 may be combined on the same day. Additionally, the Day 0 Visit may be performed over multiple visits if performed within the 28-day Screening window.
2. All scheduled study visits should be completed within the respective visit windows. If the participant is not able to attend a study site visit due to the COVID-19 pandemic (self-quarantine or disruption of study site activities following business continuity plans and/or local government mandates for “stay at home” or “shelter in place”), a safety telephone call to the participant should be made in place of the study site visit. The safety telephone call should encompass all scheduled visit assessments that can be completed remotely, such as assessment for AEs and concomitant medications (eg, as defined in scheduled safety telephone calls). Home visits will be permitted for all

nondosing visits, except for Screening, if a participant cannot visit the study site due to the COVID-19 pandemic. Home visits must be permitted by the study site IRB and the participant via informed consent/assent and have prior approval from the Sponsor (or its designee).

3. If the visit for the second dose (Day 29) is disrupted and cannot be completed at Day 29 +7 days due to the COVID-19 pandemic (self-quarantine or disruption of study site activities following business continuity plans and/or local government mandates for “stay at home” or “shelter in place”), the visit window may be extended to Day 29 + 21 days. When the extended visit window is used, the remaining study visits should be rescheduled to follow the inter-visit interval from the actual date of the second dose.
4. Safety follow-up via an eDiary questionnaire will be performed every 4 weeks from Day 71 to Day 183 and again from Day 223 to Day 363.
5. Safety follow-up via a safety telephone call will be performed every 4 weeks from Day 85 to Day 197 and again from Day 237 to Day 377.
6. The Participant Decision Visit may be performed over multiple visits. Once the Participant Decision Visit has been initiated, all assessments must be completed within a 7-day period.
7. Physical examination: A full physical examination, including height and weight, will be performed at Day 1, Day 29, Day 57, Day 209, and Day 394. BMI will be calculated only at Screening Visit (Day 0). Symptom-directed physical examinations may be performed at other timepoints at the discretion of the investigator. On each injection day before injection and again 7 days after injection, the arm receiving the injection should be examined and the associated lymph nodes should be evaluated. Any clinically significant finding identified during a study visit should be reported as a MAAE. Vital signs are to be measured predose and postdose on days of injection (Day 1 and Day 29). When applicable, vital signs should be measured before blood collection. Participants who are febrile (body temperature $\geq 38.0^{\circ}\text{C}/100.4^{\circ}\text{F}$) before injection on Day 1 or Day 29 must have the visit rescheduled within the relevant visit window to receive the injection. Afebrile participants with minor illnesses can be enrolled at the discretion of the investigator.
8. Pregnancy test at Screening and Day 1 and before the second study injection will be a point-of-care urine test. At the discretion of the investigator, a pregnancy test either via blood or point-of-care urine test can be performed at any time.
9. Sample must be collected prior to dosing of injection on Day 1.
10. The nasopharyngeal or nasal swab sample will be used to ascertain the presence of SARS-CoV-2 via RT-PCR.
11. An unscheduled visit may be prompted by reactogenicity issues, illness visit criteria for COVID-19, or new or ongoing AEs. If a participant meets the prespecified criteria of suspicion for COVID-19 ([Section 7.1.6](#)), the participants will be asked to return within 72 hours or as soon as possible to the study site for an unscheduled illness visit, to include an NP or nasal swab sample (for RT-PCR testing) and other clinical evaluations. If a study site visit is not possible, a home visit may be arranged to collect the NP or nasal sample and conduct clinical evaluations. If a home visit is not possible, the participant will be asked to submit a saliva sample to the study site by a Sponsor-approved method. At this illness visit, the NP or nasal swab samples will be collected to evaluate for the presence of SARS-CoV-2 infection. NP or nasal swab samples will also be tested for the presence of other respiratory pathogens. If due to COVID-19 related restrictions in the community, the participant’s LAR performed a home test rather than obtaining a test performed by a health care professional, see [Section 7.1.6](#). In addition, the study site may collect an additional NP or nasal sample for SARS-CoV-2 testing to be able to render appropriate medical care for the study participant as determined by local standards of care. Additionally, clinical information will be carefully collected to evaluate the severity of the clinical case.
12. A convalescent visit will be scheduled approximately 28 days (+7 days) after diagnosis. At this visit, an NP or nasal swab sampling for viral PCR and a blood sample will be collected for potential immunologic assessment of SARS-CoV-2 infection.
13. Diary entries will be recorded by the participant at approximately 30 minutes after injection while at the study site with instruction provided by study staff. Study participants will continue to record entries in the eDiary each day after they leave the study site, preferably in the evening, on the day of injection and for 6 days following injection. If a solicited local or systemic AR continues beyond Day 7 after vaccination, the participant will be prompted to capture details of the solicited local or systemic AR in the eDiary until the AR is resolves or the next IP injection occurs, whichever occurs first; capture of details of ARs in the eDiary should not exceed 28 days after each vaccination. ARs recorded in eDiaries beyond Day 7 should be reviewed either via telephone call or at the following study visit.
14. Trained study site personnel will call all participants to collect information relating to any AEs, MAAEs, SAEs, AEs leading to study withdrawal, information on concomitant medications associated with those events, and any nonstudy vaccinations. In addition, study personnel will collect information on known participant exposure to someone with known COVID-19 or SARS-CoV-2 infection and on participant experience of COVID-19 symptoms.
15. All concomitant medications and nonstudy vaccinations will be recorded through 28 days after each injection; all concomitant medications relevant to or for the treatment of an SAE or MAAE will be recorded from Day 1 through the final visit (Day 394).

Table 11: Participant Decision Clinic Visit

	All Participants
Return to clinic for Participant Decision Clinic Visit	X
Sign revised Informed Consent Form	X
Confirm participant's choice to be unblinded or not to be unblinded	X
Confirm participant's choice to receive open-label mRNA-1273	X
Nasopharyngeal or nasal swab	X
Blood for immunologic analysis	X
Counsel about public health measures to limit virus spread ¹	X

¹. All participants are counseled about the importance of continuing other public health measures to limit the spread of disease including physical-social distancing, wearing a mask, and hand-washing.

[figure not shown]
Figure 10: Schedule of Part 1A and Part 1B Participant Visits During the Part 1B Open-label Period

Table 12: Schedule of Assessments Part 1B, Open-label Observational Phase for Participants Who Previously Received Placebo

Visit Number	7	8	9	10	11
Type of Visit	C	C	C	SC ⁸	C
Study Visit Day	(~D209/ Participant Decision Visit) OL-D1	OL-D29	OL-D57 ²	OL-D113	OL- D178 ⁹
Window Allowance (Days)	-56/+56 ¹	-3/+7	±14	± 3	±14
Days Since Most Recent Injection	0	28	28	84	149
Informed consent form	These assessments are already performed as part of the regular D209 Visit.				
Blood for vaccine immunogenicity			X		X
Nasopharyngeal or nasal swab sample for SARS-CoV-2 ³		X	X		
Physical examination including vital signs ⁴	PE including vitals performed as part of D209 Visit.	X	X		X
	X Vitals obtained post dose.	X			
Pregnancy testing	X	X			
Study injection (including 30-minute postdosing observation period)	X	X			
Informed consent for BD			X ⁷		
Recording of MAAEs and concomitant medications relevant to or for the treatment of the MAAE ⁵	X	X	X	X	X
Recording of SAEs and concomitant medications relevant to or for the treatment of the SAE ⁵	X	X	X	X	X
Recording of AESI	X	X	X	X	X
Recording of concomitant medications and nonstudy vaccinations ⁵	X	X	X	X	X
Surveillance for COVID-19/ Illness visit ⁶ / Unscheduled visit	X	X	X	X	X
Study completion (for Part 1B)					X

Abbreviations: AE = adverse event; AESI = adverse event of special interest; BD = booster dose; C = clinic visit; COVID-19 = coronavirus disease 2019; D = Day; M = month; MAAE = medically attended AE; NP = nasopharyngeal; OL = open-label; PCR = polymerase chain reaction; RT-PCR = reverse transcriptase polymerase chain reaction; SAE = serious adverse events; SARS-CoV-2 = Severe Acute Respiratory Syndrome coronavirus 2; SC = safety (telephone) call.

1. The Participant Decision Visit may be performed over multiple visits. Once the Participant Decision Visit has been initiated, all assessments must be completed within a 7-day period.
2. After the OL-D57 visit, Part 1B participants who choose to receive BD will have one additional safety call at OL-D113 prior to entering Part 1C-1.
3. The NP or nasal swab sample, collected prior to vaccination on days of injection, will be used to ascertain the presence of SARS-CoV-2 via PCR.
4. Physical examination: A symptom-directed physical examination will be performed at OL-D1, OL-D29, OL-D57, and OL-D178. Symptom-directed physical examinations may be performed at other timepoints at the discretion of the investigator. Any clinically significant finding identified during a study visit should be reported as a MAAE. Vital signs are to be collected predosing and postdosing on days of injection (OL-D1 and OL-D29). When applicable, vital sign measurements should be performed before blood collection. Participants who are febrile (body temperature $\geq 38.0^{\circ}\text{C}/100.4^{\circ}\text{F}$) before injection on OL-D1 or OL-D29 must be rescheduled within the relevant window period to receive the injection. Afebrile participants with minor illnesses can be administered investigational product at the discretion of the investigator.
5. All concomitant medications and nonstudy vaccinations will be recorded throughout the study; all concomitant medications relevant to or for the treatment of an SAE or MAAE will be recorded from Day 1 through OL-D113 before entering Part 1C-1. If a participant declines a BD, all concomitant medications relevant to or for the treatment of an SAE or MAAE will be recorded from Day 1 through OL-D178.
